### **c) Local Number of Subjects**

An average of 10 breast reductions are performed monthly at Temple University Hospital. We expect nearly all of these patients to meet screening criteria and to agree to participate in this study

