### **d) Study-Wide Number of Subjects**

This is a single site study. Anticipated number of subjects is approximately 60

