### **g) Procedures Involved in the Human Research**

Study subjects will undergo breast surgery by the individual surgeon's standard technique. No changes in surgical technique will occur as part of this study. Regional nerve block with bupivacaine and/or lidocaine is typically offered to patients as part of this procedure and is considered standard of care. However, not all patients opt to receive a nerve block

For the study, subjects will be randomized to experimental and control groups in a ratio of 1:1. Randomization will occur upon enrollment in the study. When the patient is enrolled, the investigator will use the Sealed Envelope™ simple randomization tool to assign the subject a treatment group. Randomization occurs in random permuted blocks to achieve an even distribution between groups. Patients will be blinded to their study group.

All subjects will receive perineural nerve block in the preoperative holding area prior to the case performed by faculty from the anesthesia pain service. An ultrasound guided pecs block will be performed. For the block, the fascial plane separating the pectoralis major and pectoralis minor muscles is identified by ultrasound at the level of the 3rd rib. A needle is advanced into this space and the local anesthetic is infiltrated. The experimental group will receive 29cc 0.5% bupivacaine mixed with 1mL 4mg/mL dexamethasone for each side (40 cc total). The control group will receive 29cc 0.5% bupivacaine mixed with 1mL 0.9% saline solution for each side.

All patients will undergo standard breast reduction with no change in the standard operative technique.

All patients will receive a standard postoperative pain regimen as follows:

- Percocet 5/325 1 tab q4hr prn pain (moderate, 4 – 7)
- Percocet 5/325 2 tabs q4hr prn pain (severe, 8 – 10)
- IV 1mg Morphine q1hr prn breakthrough pain
- IV 4mg Zofran q8hrs prn N/V

This may be adjusted for patient drug allergies

Bupivacaine is a local analgesic used routinely during surgical procedures. It is FDA approved for this indication.

Dexamethasone is a glucocorticoid available in oral and intravenous formulations. It is FDA approved for a multitude of anti-inflammatory indications. While off label, it is standard of care to provide IV

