## Enhanced pain control after reduction mammoplasty with bupivacaine and dexamethasone regional block

Data will be extracted from the Epic electronic medical record. Consultation with medical informatics has been obtained to assist with development of an automated data collection mechanism. Data will be stored in a spreadsheet that allows for manipulation and analysis. Patient surveys will be conducted a week after the procedure and documented on paper and the responses will be manually inputted into an electronic database (REDCap). Survey responses (REDCap) will be matched to inpatient data measurements (Epic) through study ID numbers. The spreadsheet itself will be encrypted and will be stored exclusively on hospital network databases.

The two groups will be compared using a Student T test to evaluate for significant differences in the endpoints of each group.

A 2 mean 2 sided power analysis was conducted assuming the mean VAS difference between groups to be 1.5. A sample size of 30 in each group will have 81% power to detect a difference in means of 1.500 assuming that the common standard deviation is 2.000 using a two group t-test with a 0.050 two-sided significance level. We anticipate using larger numbers to power subgroup analysis.

Analysis between the two groups will involve a linear mixed effect model to compare the pain scales of the two groups over time. If vital signs are dissimilar at the beginning of the study, they will be controlled for prior to analysis. Pain medication requirement (determined by quantity of pills or mg used of same medication) will also be controlled within the analysis model. Adjustments to the pain score within the groups due to pain medication usage will be performed.

However, need for postoperative anti-emetic therapy is expected to be a somewhat rare event with similar means. In a similar power analysis with an expected group A mean of 0.5 doses and group B mean of 1 dose with standard deviation of 1, a sample size of 63 is required to reach significance. A somewhat large standard deviation is expected given the need for repeated dosing in those who do experience post-operative nausea

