Similarly, length of hospital stay is expected to be similar between the two groups. The difference is generally expected to be between a “before lunch” or “after lunch” discharge on post-operative day 1. A two-group t test with a 0.05 two-sided significance level will be used to evaluate a difference in length of hospital stay. Therefore, a 2 mean 2 sided power analysis assuming group A mean hospital stay of 16 hours and group B mean stay of 18 hours with 4 hour standard deviation, a sample size of 63 is required to achieve 80% power with  $p < 0.05$ .

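### The sample size of 63 for length of stay gives 80% power only if it means 63 per group (126 in total); the planned total of about 60 gives about 48%

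*Combined protocol and SAP*

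**What the plan says.** Three sample-size statements stand in section 10(i), Data Management, of the combined protocol and SAP.

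- **VAS pain score (primary):** "A sample size of 30 in each group will have 81% power to detect a difference in means of 1.500", with a standard deviation of 2. This figure is labelled per group.
- **Antiemetic doses (secondary):** means of 0.5 and 1 dose with a standard deviation of 1, for which "a sample size of 63 is required to reach significance". Neither a power nor a per-group or total label is given.
- **Length of stay (secondary):** "group A mean hospital stay of 16 hours and group B mean stay of 18 hours with 4 hour standard deviation", tested by a two-group t-test at two-sided 0.05, for which "a sample size of 63 is required to achieve 80% power with" p < 0.05. Again there is no label.

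On enrolment, section 10(d) says "Anticipated number of subjects is approximately 60", and section 10(g) says "subjects will be randomized to experimental and control groups in a ratio of 1:1". That makes about 30 per group. Section 10(i) also remarks: "We anticipate using larger numbers to power subgroup analysis". It gives no number.

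**The concern.** The VAS figure carries a per-group label and the two figures of 63 do not. The only enrolment target is about 60 in total, so an unlabelled 63 looks like a requirement that the trial nearly meets. If the figure is per group, the requirement is about twice the target, and nothing in the document says so.

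This matters when the results are read. With a true chance of success near one half, a non-significant result for length of stay says little. A reader relying on the printed 80% could take it as evidence of no effect. For antiemetic use the reader cannot tell what power, if any, the 63 refers to. No sample size guarantees significance; it only sets the probability of reaching it.

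**Working it through.** **Inputs.** Length of stay: difference 18 − 16 = 2 h, SD 4 h, two-sided alpha 0.05, power 80% (section 10(i)). Antiemetic doses: difference 1 − 0.5 = 0.5, SD 1 (section 10(i)). Planned total about 60 (section 10(d)), allocated 1:1 (section 10(g)).

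**Standardised difference.** 2/4 = 0.5 for length of stay and 0.5/1 = 0.5 for antiemetic doses. The two calculations are therefore the same.

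**Reproducing the plan's figure.** By the normal approximation,

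n per group = 2 × (1.960 + 0.842)² / 0.5² = 62.79, rounded up to 63.

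The noncentral t calculation gives 63.77, so 64 per group. The plan's 63 is thus correct as a per-group number, and the total is 2 × 63 = 126 (128 by the t calculation).

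**Power at the sizes in question** (standardised difference 0.5, two-sided 0.05):

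| Patients | t-test | Normal approximation |
|---|---|---|
| 30 per group (planned total of 60) | 47.8% | 49.1% |
| 63 in total (31 + 32) | 49.7% | 51.0% |
| 60 per group (120 in total) | 77.5% | 78.2% |
| 63 per group (126 in total) | 79.5% | 80.1% |
| 64 per group (128 in total) | 80.1% | 80.7% |

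A simulation of 200,000 trials at 30 per group also gave 47.8%.

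**Detectable difference at 30 per group, 80% power (t-test).** 0.736 SD: 0.736 × 4 = 2.94 h against the assumed 2 h, and 0.736 × 1 = 0.74 doses against the assumed 0.5.

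**Planned against required.** 60/126 = 48%. That this ratio matches the power is a coincidence.

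**Antiemetic wording taken literally.** If the sentence means the size at which an observed difference of 0.5 SD just gives p < 0.05, the answer is a total: 31 + 31 gives p = 0.049 by the normal test, and 32 + 32 gives p = 0.0499 by the t-test. So 62 to 64 in total also lies close to 63. The per-group, 80% reading is the likelier one, because the plan presents this calculation as akin to the VAS power analysis and it has the same inputs in SD units as length of stay. The text does not settle it.

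**Check on the primary endpoint.** 1.5/2 = 0.75; at 30 per group the t-test power is 81.5%, in agreement with the stated 81%.

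**The case against.** The strongest reply is that nothing was miscalculated: 63 is exactly what the normal formula gives per group, and no reading as a total reaches 80%. Read in order, after a VAS figure labelled per group, 63 is naturally compared with 30. The linking words around the two calculations present these endpoints as harder to show than VAS. Both endpoints are secondary, and a trial sized on its primary endpoint need not be powered for them. The target of 60 is also approximate. Section 10(c) says "An average of 10 breast reductions are performed monthly", which over 12 months (section 10(e)) is 10 × 12 = 120 cases, and at 60 per group the power would be 77.5%.

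Much of this stands. The fault is a missing label and an undisclosed shortfall, not a wrong formula, and the difference between 63 and 64 is only one of method. Nor do secondary endpoints have to be powered. But the plan chose to print sizes for them, and those must be interpretable. The linking words hint at a need for more patients without giving the gap. The larger numbers mentioned are unquantified and tied to subgroup analysis. The 120 cases are surgical volume, not an enrolment target, and even enrolling every one would fall short of 126.

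One caveat on antiemetic use also stands. Doses are skewed counts, so the t-test figure is approximate. A simulation with the stated means and SDs, assuming negative binomial counts in one group and Poisson in the other, gave about 51% at 30 per group. The conclusion does not change.

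**Conclusion.** The concern holds. The 63 for length of stay delivers 80% power only as 63 per group, 126 in total. The one stated target, about 60 in total, delivers about 48% for the assumed 2-hour difference. The same applies to antiemetic doses if their 63 is also per group with 80% power, which is likely but not stated.

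These figures rest on the plan's own means and standard deviations, equal allocation, a two-sided 5% t-test and complete data; the plan states no dropout allowance, and losses would lower the power further. They would improve only if a larger target were set. The primary VAS sizing is not affected, so this should be fixed but does not threaten the main comparison.

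**What to change.** In section 10(i):

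1. Label the length-of-stay figure as 63 per group, 126 in total (64 per group if computed for the t-test).
2. Label the antiemetic 63 as per group, if that was intended, and replace the phrase about significance with the power that was assumed.
3. Add one sentence: with approximately 60 patients, power for these two secondary endpoints is about 48% for the assumed differences; the differences detectable with 80% power are about 2.9 hours and 0.74 doses; results will be reported with 95% confidence intervals. The intervals are not needed to correct the label, but they let a reader see what a non-significant result does and does not exclude.

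The cost is a text edit and a less favourable stated power for two secondary endpoints. No patients are added, and the VAS calculation stays as it is.

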## Enhanced pain control after reduction mammoplasty with bupivacaine and dexamethasone regional block

### **j) Confidentiality**

All patient data will be deidentified prior to storage. Data will be stored in an encrypted electronic database. Only study personnel will have access to this database. No one will be permitted to store the database on a personal device. The database will be stored exclusively on hospital network servers.

### **k) Provisions to Monitor the Data to Ensure the Safety of subjects**

No significant risk is anticipated by the proposed study interventions. All of the medications are currently in routine use at this institution. All adverse events related to study medication will be evaluated by the primary investigator. A MIDAS report will be filed for any adverse event. If there are any occurrences, an interim summary of adverse events will be compiled at 1 month and provided to the IRB.

The study will be terminated immediately if study interventions result in subjects requiring intensive care interventions or death.

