### **f) Study Endpoints**

Primary study endpoints are average VAS pain score during hospitalization and postoperative narcotic usage during the hospitalization. Secondary endpoints are need for antiemetic therapy, length of hospitalization, and aggregate pain and quality of

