### **11) Risks to Subjects**

Regional nerve block is an optional component of the standardly performed breast reduction at this institution. Participation in the study does entail all the standard risks of this procedure. These are primarily bleeding or bruising at the injection site, nerve damage resulting in pain, numbness or weakness, infection, and

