## Enhanced pain control after reduction mammoplasty with bupivacaine and dexamethasone regional block

inadvertent systemic injection of the anesthetic. There is a very small risk of pneumothorax.

Primary additional risk to subjects compared to the standardly practiced block is allergic or adverse reaction to the study medication posed by the administration of dexamethasone. Adverse effects of this medication include behavioral disturbance, cardiac arrhythmia, hyperglycemia, and immune suppression. There is additional risk of increased postoperative pain due to deviation from standard nerve block procedure.

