### **13) Privacy and Confidentiality**

All PHI will be removed prior to storage of any patient information. PHI will not be shared with any research personnel or any other persons. Randomization status and all medications received will be disclosed to all healthcare personnel involved in the patient's care while in the hospital. The patient will not be informed of his or her study group. Patients will be completely informed of all privacy procedures as part of the consent process. Study personnel will be available to answer questions throughout the duration of the study.

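### Investigator review covers only adverse events already linked to the study drug, with no stated assessor, criteria or masking, and no comparison of harm by arm is planned

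*Combined protocol and SAP*

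**What the plan says.** All references are to the combined protocol and SAP.

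- **Investigator review, section 10(k):** "All adverse events related to study medication will be evaluated by the primary investigator".
- **Reporting, same section:** "A MIDAS report will be filed for any adverse event". The section also provides, for the case that events have happened, that "an interim summary of adverse events will be compiled at 1 month and provided to the IRB". Neither step is limited to drug-related events.
- **Knowledge of the arm, section 13:** "Randomization status and all medications received will be disclosed to all healthcare personnel involved in the patient's care while in the hospital". Section 10(g) adds only: "Patients will be blinded to their study group".
- **Named risks, section 11:** the list for the block begins "These are primarily bleeding or bruising at the injection site, nerve damage resulting in pain, numbness or weakness, infection, and"; it goes on to name accidental systemic injection and, as very unlikely, pneumothorax. For dexamethasone, "Adverse effects of this medication include behavioral disturbance, cardiac arrhythmia, hyperglycemia, and immune suppression".
- **Endpoints, section 10(f):** "Primary study endpoints are average VAS pain score during hospitalization and postoperative narcotic usage during the hospitalization". The secondary endpoints are antiemetic need, length of stay and survey scores. Adverse events appear in neither list.

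**The concern.** Relatedness is normally a conclusion reached after an event has been recorded and looked at. Here it decides which events the investigator looks at. Several risks in section 11 could plausibly be put down to something other than the drug. Bleeding, nerve damage and pneumothorax are presented there as risks of the block procedure. Infection, an arrhythmia or a behavioral change after an operation under anesthesia has other possible explanations. Someone has to make that call before the investigator is involved, and the plan does nothing to keep that person unaware of the arm. If knowing the arm affects the call, the same event could be reviewed in a dexamethasone patient and passed over in a control.

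At stake is the account of harm. Dexamethasone is the only planned difference between the arms, and section 11 describes reactions to it as the main added risk. The trial should at least be able to report what happened in each arm on the same footing.

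**Working it through.** The plan gives no adverse-event rate, attribution rate or safety sample size, so there is no figure of its own to reproduce. The check is mainly a reading of the passages against each other.

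1. **Who enters review.** Section 10(k) admits drug-related events only. No section names the person who decides, gives criteria or requires masking. Section 10(f) relies on the same kind of attribution when it ends participation after an adverse reaction to the study medication.

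2. **Who is masked.** Section 10(g) masks patients and section 13 unmasks care staff. In section 10(g) the investigator runs the randomization tool, and in section 10(h) the PI and coordinator hold the file linking identity to study ID. No masked assessor is described, so unmasked attribution is likely, though it is not stated.

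3. **What happens to other events.** They receive a MIDAS report and can enter the IRB summary. They leave investigator evaluation, not all recording.

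4. **Whether those records reach the analysis.** Sections 10(g) and 10(i) name two data sources: Epic, and paper surveys entered in REDCap. MIDAS is not one of them. The instruments at the first post-operative visit are pain and quality-of-life questionnaires, and no query about the section 11 risks is described. No section defines an adverse event or sets a collection window.

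5. **Whether harm is compared.** The t test in section 10(i) applies to the endpoints, which do not include adverse events. The only summary of adverse events is the one at 1 month, and it is not stated to be by arm.

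6. **Reach of the 1-month summary.** Assume the month runs from first enrolment, which the text does not say. Section 8 gives about 10 procedures a month, nearly all expected to enroll. Spreading the 60 subjects of section 10(d) over the 12 months of section 10(e) gives 60 / 12 = 5 a month. The summary would then cover about 5 to 10 of 60 subjects, or 8% to 17%.

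7. **What a table by arm could show.** With 30 per arm (section 10(i)) and no events of a given type in one arm, the one-sided 95% upper limit on the true risk is 1 − 0.05^(1/30) = 0.095, or 9.5%. A table would be descriptive and could not exclude modest differences.

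8. **Vital signs.** The Abstract lists them as a secondary endpoint and section 10(f) does not. Section 10(i) mentions them only as a possible adjustment for differences at the start of the study.

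**The case against.** The strongest reply is that the sentences following the review rule already catch the rest: MIDAS takes any adverse event and the IRB sees a summary. That is correct, and it limits the point to evaluation and analysis.

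A reader might go further and infer that attribution is left to staff who know the arm. The documents do not say so. Section 13 tells care staff the arm but gives them no role in judging relatedness, and the only person section 10(k) names is the primary investigator. Unmasked attribution is a reasonable inference and no more.

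A reader might also infer that harm cannot be compared at all. That is too strong, because MIDAS reports or Epic entries could be tabulated by arm later. The gap is that the plan does not provide for this, or for asking about the listed risks in the same way in both arms.

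Other replies also carry weight:

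- The database contents in section 10(h) are given as examples, so their silence on adverse events proves nothing.
- The scope of the term for study medication is unclear. Sections 10(b) and 18 use the plural, and both arms receive bupivacaine, so some control events, including systemic injection of the anesthetic, may fall inside the rule.
- The objective in section 5 is analgesia and narcotic need, and no safety comparison is promised.
- With about 30 per arm, even complete capture would seldom settle a question of harm.

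These replies lower the stakes. They do not supply an assessor, criteria, masking, a collection window or a table by arm.

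**Conclusion.** The point holds in a limited form. Investigator evaluation depends on a prior judgement of relatedness that has no stated assessor, criteria or masking, in a trial where only patients are blinded. Events outside that judgement are still reported, but nothing planned brings them into the study data or compares them by arm. The plan therefore specifies no valid comparison of harm.

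No size can be put on any attribution bias, because the documents contain no rates from which to derive one. The conclusion rests on the text alone. It does not require that bias will occur, only that the plan does not guard against it. This should be changed, but it does not threaten the primary pain comparison, and correcting it will not make a trial of about 60 subjects able to establish or exclude modest differences in harm.

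**What to change.** Replace the review sentence in section 10(k) with wording to this effect: all adverse events from the block to the first post-operative visit, including each risk listed in section 11, will be recorded in the study database in both arms and evaluated whatever the suspected cause. Then:

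- Judge relatedness afterwards, from a summary with the arm removed. Where possible, use an existing study physician who neither assigned nor treated that patient, since sections 10(g) and 10(h) may leave the PI unmasked. Section 8 expects at least 5 project staff, led from two departments, which should make this workable.
- Tabulate all events descriptively by arm whatever the attribution, and state that about 30 per arm cannot establish or exclude modest differences.
- Name adverse events among the database contents in section 10(h).
- Reconcile vital signs between the Abstract and section 10(f).

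The MIDAS reports and the IRB summary can stay as they are. The cost is protocol wording, a short adverse-event form, some physician time for the masked review, and more minor events to log.
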